#### **15.4. Subject Insurance and Finance**

Noven will provide the insurance in accordance with local guidelines and requirements as a minimum for the subjects participating in this study. Details on finance and insurance will be provided in a separate agreement between the investigator and the sponsor.

## 18. APPENDICES

### 18.1. Western Ontario and McMaster Universities Osteoarthritis (WOMAC) LK3.1 Index

Copyright©1996 Nicholas Bellamy  
All Rights Reserved

[figure not shown]
English for USA - V2

WOMAC LK3.1 QUESTIONNAIRE

WOMAC

Section A

PAIN

Copyright©1996 Nicholas Bellamy  
All Rights Reserved

[figure not shown]
English for USA - V2

**WOMAC LK3.1 QUESTIONNAIRE**

**WOMB**

**Section B**

**STIFFNESS**

Copyright©1996 Nicholas Bellamy  
All Rights Reserved

English for USA - V2

**WOMAC LK3.1 QUESTIONNAIRE**

**WOMC1-3**

**Section C**

**DIFFICULTY PERFORMING DAILY ACTIVITIES**

[figure not shown]
Copyright©1996 Nicholas Bellamy  
All Rights Reserved

English for USA - V2

**WOMAC LK3.1 QUESTIONNAIRE**

**WOMC2-3**

**DIFFICULTY PERFORMING DAILY ACTIVITIES**

[figure not shown]
Copyright © 1998 NICHOLS PUBLISHING  
All Rights Reserved

English for USA - V2

**WOMAC LK3.1 QUESTIONNAIRE**

**WOMC3-3**

**DIFFICULTY PERFORMING DAILY ACTIVITIES**

[figure not shown]
Copyright©1996 Nicholas Bellamy  
All Rights Reserved

English for USA - V2

## 18.2. 11-Point Numeric Rating Scale (NRS)

*This is a sample of the Numerical Rating Scale. Please use the rating scale provided in the study reference manual.*

**Instructions:** Show the pain scale to the subject and explain that on the 0 to 10 pain rating scale, 0 means no pain and 10 means the worst possible pain. A value in the middle of the scale (around 5) would be moderate pain; a value of 2 or 3 would be mild pain and a value of 7 or higher is considered severe pain.

*Adapted from:* Farrar JT, Young JP, La Moreaux L, Werth JL, and Poole MR: Clinical importance of changes in chronic pain intensity measured on an 11-point numerical pain rating scale. Pain 2001;94:149–158.

### 18.3. Mini-OA Knee and Hip QOL (Mini-OAKHQOL)

## Quality of life in osteoarthritis of lower limbs

### Mini-OAKHQoL

*Quality of Life in Rheumatology Group* © 2012

**Please read the following instructions carefully:**

*The following statements refer to the impact your knee and/or hip osteoarthritis has had on your quality of life. This information allows us to better understand how you are living on a daily basis with your osteoarthritis.*

☞ Check the response that best describes your situation,

between “**not at all**” and “**absolutely**”,  
between “**not at all**” and “**a great deal**”,  
between “**never**” and “**all the time**”  
according to each of the proposed statements.

There is no right or wrong answer.

☞ For each statement check only one response (☒)

**Example:**

I have difficulty climbing stairs.	Not at all					A great deal					
											
	0	1	2	3	4	5	6	7	8	9	10

**Date completed:** |\_\_|\_\_| |\_\_|\_\_| |\_\_|\_\_|\_\_|

**THIS QUESTIONNAIRE CONSISTS OF THREE PAGES (INCLUDING THIS ONE).**

*Quality of Life in Rheumatology Group* © 2012  
Version 1.1

**Read these questions one by one paying attention to your quality of life  
OVER THE PAST FOUR WEEKS.  
Check the response that corresponds best to the way you are living with your osteoarthritis.**

	Not at all										A great deal									
1. I have difficulty walking																				
	0	1	2	3	4	5	6	7	8	9	10									
2. I have difficulty bending down or getting up																				
	0	1	2	3	4	5	6	7	8	9	10									
3. I have difficulty climbing up stairs																				
	0	1	2	3	4	5	6	7	8	9	10									
4. I have difficulty dressing myself (socks, shoes, tights/pantyhose)																				
	0	1	2	3	4	5	6	7	8	9	10									
5. I have difficulty getting in or out of a car																				
	0	1	2	3	4	5	6	7	8	9	10									
6. I have difficulty performing my tasks at work																				
	0	1	2	3	4	5	6	7	8	9	10									
Not applicable																				
7. It takes me longer to do things																				
	0	1	2	3	4	5	6	7	8	9	10									
8. I feel unhappy because of my pain																				
	0	1	2	3	4	5	6	7	8	9	10									
9. I worry about having to depend on others																				
	0	1	2	3	4	5	6	7	8	9	10									
10. I am limited in my sexual activities																				
	0	1	2	3	4	5	6	7	8	9	10									
No sexual activity in the past 4 weeks																				

	Never										Always									
11. I have difficulty staying in the same position for a long time, (sitting, standing, being still)																				
	0	1	2	3	4	5	6	7	8	9	10									
12. I have pain (how often)																				
	0	1	2	3	4	5	6	7	8	9	10									
13. I have pain (intensity)																				
	0	1	2	3	4	5	6	7	8	9	10									

Read these questions one by one paying attention to your quality of life

OVER THE PAST FOUR WEEKS.

Check the response that corresponds best to the way you are living with your osteoarthritis.

	Not at all										Absolutely											
	0	1	2	3	4	5	6	7	8	9	10	0	1	2	3	4	5	6	7	8	9	10
14. I am able to plan long term projects																						
15. I get out of the house as much as I would like																						
	Never										All the time											
16. I wake up because of my pain																						
	0	1	2	3	4	5	6	7	8	9	10	0	1	2	3	4	5	6	7	8	9	10
17. I wonder about what I will become in the future																						
	0	1	2	3	4	5	6	7	8	9	10	0	1	2	3	4	5	6	7	8	9	10
18. I am irritable, grouchy																						
	0	1	2	3	4	5	6	7	8	9	10	0	1	2	3	4	5	6	7	8	9	10
	Not at all										A great deal											
19. I feel that others understand the difficulties I have related to my osteoarthritis																						
	0	1	2	3	4	5	6	7	8	9	10	0	1	2	3	4	5	6	7	8	9	10
20. I feel supported by those close to me (partner, family,...)																						
	0	1	2	3	4	5	6	7	8	9	10	0	1	2	3	4	5	6	7	8	9	10

Please make sure that you have checked one box and only one  
for each of the 20 statements.

Thank you for answering this questionnaire

#### 18.4. Work Productivity and Activity Impairment Questionnaire for Osteoarthritis (WPAI: OA)

**Work Productivity and Activity Impairment Questionnaire:  
Osteoarthritis of the Knee or Hip V2.0 (WPAI:OA)**

The following questions ask about the effect of your osteoarthritis of the knee or hip on your ability to work and perform regular activities. *Please fill in the blanks or circle a number, as indicated.*

1. Are you currently employed (working for pay)?  NO  YES  
*If NO, check "NO" and skip to question 6.*

The next questions are about the **past seven days**, not including today.

2. During the past seven days, how many hours did you miss from work because of problems associated with your osteoarthritis of the knee or hip? *Include hours you missed on sick days, times you went in late, left early, etc., because of your osteoarthritis of the knee or hip. Do not include time you missed to participate in this study.*

HOURS

3. During the past seven days, how many hours did you miss from work because of any other reason, such as vacation, holidays, time off to participate in this study?

HOURS

[figure not shown]
4. During the past seven days, how many hours did you actually work?

HOURS *(If "0", skip to question 6.)*

5. During the past seven days, how much did your osteoarthritis of the knee or hip affect your productivity while you were working?

*Think about days you were limited in the amount or kind of work you could do, days you accomplished less than you would like, or days you could not do your work as carefully as usual. If osteoarthritis of the knee or hip affected your work only a little, choose a low number. Choose a high number if osteoarthritis of the knee or hip affected your work a great deal.*

Consider only how much osteoarthritis of the knee or hip affected productivity while you were working.

[figure not shown]

CIRCLE A NUMBER

6. During the past seven days, how much did your osteoarthritis of the knee or hip affect your ability to do your regular daily activities, other than work at a job?

*By regular activities, we mean the usual activities you do, such as work around the house, shopping, childcare, exercising, studying, etc. Think about times you were limited in the amount or kind of activities you could do and times you accomplished less than you would like. If osteoarthritis of the knee or hip affected your activities only a little, choose a low number. Choose a high number if osteoarthritis of the knee or hip affected your activities a great deal.*

Consider only how much osteoarthritis of the knee or hip affected your ability to do your regular daily activities, other than work at a job.

CIRCLE A NUMBER

WPAI:OA V2.0 (US English)

## **18.5. Regulations**

Refer to the following United States Code of Federal Regulations (CFR):

- FDA Regulations 21 CFR, Parts 50.20 – 50.27  
Subpart B – Informed Consent of Human Subjects
- FDA Regulations 21 CFR, Parts 56.107 – 56.115  
Part 56 – Institutional Review Boards  
Subpart B – Organization and Personnel  
Subpart C – IRB Functions and Operations  
Subpart D – Records and Reports
- FDA Regulations 21 CFR, Parts 312.50 – 312.70  
Subpart D – Responsibilities of Sponsors and Investigators

## **18.6. Good Clinical Practice Guidelines**

ICH GCP guidelines can be found at the following URL:

[https://database.ich.org/sites/default/files/E6\\_R2\\_Addendum.pdf](https://database.ich.org/sites/default/files/E6_R2_Addendum.pdf)

PR	PR interval of the electrocardiogram; time duration between the P and R waves
PT	Preferred term
PGIC	Patient Global Impression of Change
PGA	Patient Global Assessment
QOL	Quality of life
QRS	QRS interval of the electrocardiogram; duration of the QRS complex
QT	QT interval of ECG, duration between the Q and T waves
OTC	Over the counter
QTcB	QT interval of ECG corrected for heart rate using Bazett's formula
QTcF	QT interval of ECG corrected for heart rate using Fridericia's formula
SAE	Serious adverse event
SAF	Safety analysis set
SAP	Statistical analysis plan
SAS®	Statistical Analysis Software
SD	Standard deviation
SMQs	Standard MedDRA Queries
SOC	System organ class
TEAE	Treatment-emergent adverse event
TLF	Table, listing, and figure
WHO	World Health Organization
WOMAC	West Ontario and McMasters Universities Osteoarthritis Index
WPAI-OA	Work Productivity and Activity Impairment Questionnaire for Osteoarthritis

Noven Pharmaceuticals, Inc.

Protocol HP-5000-US-07

1. INTRODUCTION

This statistical analysis plan (SAP) is based on protocol version 2.0, dated 07 January 2021.

2. STUDY OBJECTIVES

2.1 PRIMARY EFFICACY OBJECTIVE

The primary objective of this study is to evaluate the effect of HP-5000 on pain among subjects with Osteoarthritis (OA) of the knee at Week 12.

Primary Efficacy Endpoint for this objective is:

- West Ontario and McMasters Universities Osteoarthritis Index (WOMAC) LK3.1 OA (pain) change from baseline at Week 12

2.2 KEY SECONDARY EFFICACY OBJECTIVES

The key secondary objectives of this study are:

- To evaluate the effect of HP-5000 on physical function among subjects with OA of the knee at Week 12
- To evaluate the effect of HP-5000 on stiffness among subjects with OA of the knee at Week 12

Key Secondary Efficacy endpoints for these objectives are:

- WOMAC LK3.1 OA (physical function) change from baseline at Week 12
- WOMAC LK3.1 OA (stiffness) change from baseline at Week 12

2.2.1 OTHER SECONDARY EFFICACY OBJECTIVES

- To evaluate the effect of HP-5000 on pain among subjects with OA of the knee at Weeks 1, 2, 4, and 8
- To evaluate the effect of HP-5000 on physical function among subjects with OA of the knee at Weeks 1, 2, 4, and 8

 Noven Pharmaceuticals, Inc.

Protocol HP-5000-US-07

- To evaluate the effect of HP-5000 on stiffness among subjects with OA of the knee at Weeks 1, 2, 4, and 8
- To evaluate the effect of HP-5000 on pain intensity as measured by numeric rating scale (NRS) scores on a daily diary
- To evaluate the onset of effect of HP-5000 on pain among subjects with OA of the knee
- To evaluate the pattern of use of rescue medication in the study
- To evaluate skin irritation, discomfort, and adhesion following administration of HP-5000
- To evaluate the safety and tolerability of HP-5000
- To evaluate the effect of HP-5000 treatment on Quality of Life (QOL)

Other Secondary Efficacy Endpoints for these objectives are:

- WOMAC LK3.1 OA (pain) change from baseline at Weeks 1, 2, 4, and 8
- WOMAC LK3.1 OA (physical function) change from baseline at Weeks 1, 2, 4, and 8
- WOMAC LK3.1 OA (stiffness) change from baseline at Weeks 1, 2, 4, and 8
- WOMAC LK3.1 OA (composite score) change from baseline at Weeks 1, 2, 4, 8, and 12
- Change from baseline in pain intensity assessed on an 11-point NRS at Weeks 1, 2, 4, 8, and 12
- Change from baseline in pain intensity assessed on an 11-point NRS of a weekly average of all available daily pain scores at each week from Week 1 through 12
- Change from baseline in Patient Global Assessment (PGA) at Weeks 1, 2, 4, 8, and 12
- Patient Global Impression of Change (PGIC) at Weeks 1, 2, 4, 8, and 12
- Treatment Response: Reduction in the WOMAC LK3.1 OA Index (pain) of $\geq 30\%$, $\geq 50\%$, $\geq 70\%$, and $\geq 90\%$ at Weeks 1, 2, 4, 8, and 12
- Treatment Response: Reduction in the WOMAC LK3.1 OA Index (physical function) of $\geq 30\%$, $\geq 50\%$, $\geq 70\%$, and $\geq 90\%$ at Weeks 1, 2, 4, 8, and 12
- Treatment Response: Reduction in the WOMAC LK3.1 OA Index (stiffness) of $\geq 30\%$, $\geq 50\%$, $\geq 70\%$, and $\geq 90\%$ at Weeks 1, 2, 4, 8, and 12
- Rescue Medication Use during Treatment Phase: Proportion of subjects who used, number of days used, and total number of tablets

Noven Pharmaceuticals, Inc.

Protocol HP-5000-US-07

Statistical Analysis Plan

Page 13 of 58

- Onset of the effect: Change from baseline pain intensity assessed on an 11-point NRS
- Change from baseline in Mini-OA Knee and Hip QOL (Mini-OAKHQOL) scores at Weeks 4 and 12
- Change from baseline in Work Productivity and Activity Impairment Questionnaire for Osteoarthritis (WPAI: OA) impairment scores at Weeks 4 and 12

2.3 SAFETY OBJECTIVE

The safety objective is to evaluate the safety and tolerability of HP-5000.

Safety Endpoints associated with this objective are:

- The incidence of treatment-emergent adverse events (TEAEs), severity of TEAEs, adverse events (AEs) leading to discontinuation of the study drug, serious adverse events (SAEs), and other significant AEs
- Change from baseline in clinical laboratory tests (SI units), 12-lead electrocardiogram (ECG) findings, body weight, physical examination findings, and vital signs
- Dermal assessments: irritation, discomfort, and adhesion

2.4 ESTIMANDS

The estimand for the primary efficacy analysis is the difference between the ITT population treatment groups (HP-5000 vs. placebo) in change from baseline WOMAC pain scores at Week 12 taking into account intercurrent events using the composite strategy specified in the [section 16.1.5](#).

Discontinuation of study treatment due to reasons related to study treatment (e.g. AEs, lack of efficacy (LOE), etc.), rescue medication use within 24 hours of WOMAC pain assessment, and removal/detachment of the patch for more than 24 hours before WOMAC pain assessment are defined as intercurrent events.

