Efficacy Analyses	
Efficacy Outcome Analyses:
 
Primary Efficacy Outcome Analysis
 
The fixed-sequence procedure will be applied for primary and key secondary endpoints of this study, where the order in which the hypotheses are tested is pre-specified as following: (1) WOMAC pain, (2) WOMAC physical function, and (3) WOMAC stiffness. Testing begins with the first hypothesis (<math>H_1</math>) about WOMAC pain, and each test is carried out as long as significant results with level of significance <math>\alpha=0.05</math> are observed in all preceding tests. The fixed-sequence procedure controls the family-wise error rate because, for each hypothesis, testing is conditional upon rejecting all hypotheses earlier in the sequence.
 
All statistical tests of hypotheses in this trial will be 2-sided with a Type I Error rate of 0.05.
 
The estimand in the primary analysis for efficacy is the difference between treatment groups (HP-5000 vs. placebo) in the change from Baseline to Week 12 in WOMAC pain score in all randomized subjects from the ITT population and taking into account intercurrent events using the composite strategy. The study treatment discontinuation due to reasons related to study treatment (e.g. adverse events (AE), lack of efficacy (LOE), etc.), rescue medication drug use within 24 hours of WOMAC pain assessment, removal/detachment of the patch for more than 24 hours before WOMAC pain assessment are defined as intercurrent events.
 
Composite strategy will be applied to the stratum of subjects experiencing intercurrent events. For the intercurrent events of study treatment discontinuation due to reasons related to study treatment (e.g. adverse events (AE), lack of efficacy (LOE), etc.), the obtained WOMAC pain score will be addressed in the analysis by expecting the long-term benefit from the treatment for that patient to be zero from the time of intercurrent event. For the other intercurrent events including rescue medication drug use within 24 hours of WOMAC assessment, removal/detachment of study patch for more than 24 hours before WOMAC assessment, the obtained WOMAC pain score will not be included in the analysis.

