### **8.2.3 Premature Subject Withdrawal**

All subjects are free to withdraw from participation in the study at any time, for any reason, specified or unspecified, and without prejudice to further treatment. The criteria for enrollment are to be followed explicitly and if a subject who does not meet enrollment criteria is inadvertently enrolled, that subject should be withdrawn from the study and the Sponsor or CRO must be notified.

Subjects should not be asked to withdraw from the study because of experiencing AE, lack of efficacy, pregnancy, or lack of compliance to the clinical study protocol, etc. Those patients can stop their study treatments (for subjects who do not comply the protocol specified instructions and procedures, every effort will be made to keep them in the study after stopping treatment unless there is an adverse impact on subject safety). Discontinuation from study treatment does not automatically lead to a complete withdrawal from the study. Subjects discontinuing from study treatment are strongly encouraged to continue in the study up to the study completion (Follow-up Phone Visit, Week 13).

Subjects who decide they do not wish to remain in the study should NOT be considered withdrawn from the study UNLESS they withdraw their consent. Subjects are encouraged to return to all scheduled site and telephone visits, perform all procedures (including eDiary completion and blood draws) and follow the all requirements of the protocol (including the prohibited therapies), but without study treatment administration, until the end of the study (Follow-up Phone Visit, Week 13).

The reason for study treatment discontinuation and withdrawal from the study will be separately recorded. When the subject discontinues study treatment and/or withdraw from the study, the reason will be recorded in the medical records and eCRF using the below categories for discontinuation of study treatment and withdrawal from the study respectively.

The reasons will be grouped into three main categories: “study treatment related”, “not study treatment related”, and “uncertain” and more specific sub-categories will be described under each of the three main categories.

- Study treatment related
  - Lack of efficacy
  - Adverse events
  - Deviation from protocol (Please specify the deviation)
  - Other
- Not study treatment related
  - Adverse events
  - Prohibited Medication Use
  - Pregnancy
  - Deviation from protocol (Please specify the deviation)
  - COVID-19

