**Table 2 Prohibited Medications/Therapies**

Prohibited Medications/Therapies	Conditions
Any nonsteroidal anti-inflammatory drugs (NSAIDs) (selective or nonselective [Topical drug not for knees will be allowed]), acetaminophen (APAP) (>2 g/day), aspirin (ASA) (>81 mg/day), anticonvulsants (i.e., pregabalin and gabapentin etc.), muscle relaxants, other oral analgesics (prescription and/or over the counter [OTC]), antidepressants prescribed for the control of chronic pain syndromes, antihistamine with a sedative effect, sedatives for insomnia, topical products on the knee including methyl salicylate, camphor, menthol, methylsulfonylmethane, [REDACTED] [REDACTED] [REDACTED] capsaicin, any nonpharmaceutical therapy to relieve knee pain (physiotherapy, massage therapy, hot wax therapy, ice pack, acupuncture, thermal modalities, radiofrequency ablation, transcutaneous electrical nerve stimulation [TENS], pulsed vibration therapy, etc.), device to relieve knee pain (biofemoral bracing, kinesiotaping, modified shoes, wedged insoles etc.), hydroxychloroquine.	Prohibited during the study starting at Washout Visit
Any opioids, cannabinoids (prescribed or used recreationally), corticosteroids including oral, intra-muscular and intra-articular, topical, inhalation (a stable dose by inhalation for seasonal allergies and/or topical use for dermatologic allergies are allowed [Not allowed on the knees]), intra-articular viscosupplementation (e.g., Synvisc®), intra-articular drugs/biologics; anti-nerve growth factor agents, platelet rich plasma (PRP) injection, stem cells, prolotherapy, amniotic fluid injection, cyclosporine, lithium, or methotrexate	Prohibited during the study starting at Screening Visit
MAJOR SURGERY: Surgery to the target knee (i.e., damage/reconstruction of the anterior or posterior cruciate ligaments).  MINOR SURGERY: Surgery to the target knee defined as anything other than major surgery (as defined above)	Prohibited during the study starting at Screening Visit

Note: The investigator should contact the Medical Monitor with any concerns about the acceptability of any medication.

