#### **13.3. Analysis Populations**

The following analysis populations are planned for this study:

- Intent-to-Treat (ITT): Includes all consented and randomized subjects. Regardless of any protocol deviations and/or treatment compliance, analyses performed on the ITT set will be based on the randomized treatment assignment and all available data. The ITT will be used as the primary set for analysis of efficacy endpoints.
- Safety Analysis Set (SAF): Includes all subjects who have had at least 1 patch of double-blind study drug applied and who have at least 1 post-dose safety measurement during the Double-blind Treatment Phase. In the unlikely event that errors may have occurred in treatment arm assignments, then analyses using the SAF will be based on treatment actually received. The SAF will be used for the analysis of dermal evaluations and safety endpoints.

Inclusion in the analysis populations will be determined prior to database lock.

If a subject is randomized incorrectly or is administered the incorrect study drug, analyses of the ITT population will be based on the assigned treatment whereas all other analyses will be based on the actual treatment.

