#### **13.4.3.1 Primary Analysis**

The primary efficacy endpoint of this study is the change from Baseline to Week 12 in the WOMAC pain score, and key secondary endpoints are the change from Baseline to Week 12 in the WOMAC physical function and WOMAC stiffness. The primary analysis set is the ITT. The comparison of interest is: HP-5000 versus placebo.

The fixed-sequence procedure will be applied for primary and key secondary endpoints of this study, where the order in which the hypotheses are tested is pre-specified as following: (1) WOMAC pain, (2) WOMAC physical function, and (3) WOMAC stiffness. Testing begins with the first hypothesis ( $H_1$ ) about WOMAC pain, and each test is carried out as long as significant results with level of significance  $\alpha=0.05$  are observed in all preceding tests. The fixed-sequence procedure controls the family-wise error rate because, for each hypothesis, testing is conditional upon rejecting all hypotheses earlier in the sequence.

All statistical tests of hypotheses in this trial will be 2-sided with a Type I Error rate of 0.05.

The estimand in the primary analysis for efficacy is the difference between treatment groups (HP-5000 vs. placebo) in the change from Baseline to Week 12 in WOMAC pain score in all randomized subjects from the ITT population and taking into account intercurrent events using the composite strategy. The study treatment discontinuation due to reasons related to study treatment (e.g. adverse events (AE), lack of efficacy (LOE), etc.), rescue medication use within 24 hours of WOMAC pain assessment, removal/detachment of the patch for more than 24 hours before WOMAC pain assessment are defined as intercurrent events.

Composite strategy will be applied to the stratum of subjects experiencing intercurrent events.

For the intercurrent events of study treatment discontinuation due to reasons related to study treatment (e.g. adverse events (AE), lack of efficacy (LOE), etc.), the obtained WOMAC pain score will be addressed in the analysis by expecting the long-term benefit from the treatment for that patient to be zero from the time of intercurrent event. For the other intercurrent events including rescue medication use within 24 hours of WOMAC assessment and removal/detachment of study patch for more than 24 hours before WOMAC assessment, the obtained WOMAC pain score will not be included in the analysis.

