5.1 INTENT-TO-TREAT SET[ITT]

Intent-to-treat (ITT) analysis set includes all consented and randomized subjects. Regardless of any protocol deviations and/or treatment compliance, analyses performed on the ITT set will be based on the randomized treatment assignment and all available data. The ITT set will be used as the primary set for analysis of primary and secondary efficacy endpoints. If a subject is randomized incorrectly or is administered the incorrect study drug, analyses of the ITT set will be based on the assigned treatment whereas all analyses of the safety analysis set will be based on the actual treatment.

Noven Pharmaceuticals, Inc.

Protocol HP-5000-US-07

Statistical Analysis Plan

Page 17 of 58

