16.1.4 COMPOSITE STRATEGY ANALYSIS FOR PRIMARY EFFICACY

Composite strategy will be applied to the stratum of subjects experiencing intercurrent events.

For the intercurrent events of study treatment discontinuation due to reasons related to study treatment (AE, LOE, etc.), the obtained WOMAC pain score will be addressed in the analysis by expecting the long-term benefit from the treatment for that subject to be zero from the time of intercurrent event. For the other intercurrent events, rescue medication use within 24 hours of WOMAC assessment, removal/detachment of study patch for more than 24 hours before WOMAC assessment, the obtained WOMAC pain score will not be included in the analysis.

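### Should WOMAC scores taken under a prohibited analgesic be excluded from the primary analysis, as scores near rescue acetaminophen are?

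*SAP*

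**What the plan says.** Protocol version 2.0 (Synopsis and 13.4.3.1) and the SAP (2.4, 16.1.3 to 16.1.5) use the same three intercurrent events. After treatment-related discontinuation, SAP 2.4 lists "rescue medication use within 24 hours of WOMAC pain assessment, and removal/detachment of the patch for more than 24 hours before WOMAC pain assessment". The protocol synopsis gives "rescue medication drug use within 24 hours of WOMAC pain assessment, removal/detachment of the patch for more than 24 hours" beside treatment-related discontinuation, and 13.4.3.1 closes its list with "removal/detachment of the patch for more than 24 hours before WOMAC pain assessment are defined as intercurrent events". SAP 16.1.5 adds lack of compliance and protocol deviation to the first event, but only as reasons for discontinuing.

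For rescue use and patch removal, SAP 16.1.4 says "the obtained WOMAC pain score will not be included in the analysis".

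Protocol Table 2 prohibits NSAIDs, opioids, other oral analgesics and several topical products on the knee. Their use while the patch is worn is not listed as an intercurrent event. SAP 5.1 says "analyses performed on the ITT set will be based on the randomized treatment assignment and all available data", and protocol 13.3 opens the same rule with "Regardless of any protocol deviations and/or treatment compliance". Such a score is therefore analysed as observed.

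These scores can arise. Protocol 8.2.3 says subjects should not be asked to leave the study for "lack of compliance to the clinical study protocol, etc. Those patients can stop their study treatments", and it asks sites to keep them in follow-up.

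**The concern.** Two scores affected by an analgesic are handled in opposite ways. A score within 24 hours of rescue acetaminophen is removed; one taken under ibuprofen, for example, is kept. Protocol 7.2 justifies the rescue restrictions by the need to keep the pain assessments free of confounding, so the asymmetry looks like an oversight.

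The contrast is sharper because rescue is itself barred from Baseline to Visit 4, in the two calendar days before Visits 5 to 8, and on visit days. Rescue close to a scheduled WOMAC is then also a deviation, yet its score is removed. Nor is it explicit whether acetaminophen from the subject's own supply counts as rescue. Protocol 9.11 restricts rescue to sponsor tablets, and the recording source differs between 9.11 (eDiary) and 10.3.1.5 (concomitant medication eCRF).

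At stake are the clarity of the estimand and possibly some bias. If placebo subjects take more prohibited analgesics, their Week 12 pain is lowered and the treatment difference shrinks. If HP-5000 subjects took more, the bias would favour the drug. The imputation analyses do not touch observed scores, and the supplementary MMRM in 16.1.6 does not isolate these. The key secondary endpoints inherit the same handling.

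**Working it through.** **Text.** The three events do not include on-patch prohibited-analgesic use, and no wording elsewhere in the plan brings it in. The ITT rule covers it: deviations and non-compliance do not remove data. That is a treatment-policy strategy without the name.

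**Inputs.** Alpha 0.05 two-sided, 80% power and 1:1 allocation come from the documents. Effect size and N are redacted, and no usage rates or analgesic relief are given, so the rest is assumed: true difference 1.0 point, SD 3.5, relief r of 2 or 3 points, placebo use of 3%, 5% or 10%, and use rising with pain by the same function in both arms (logistic slope 1 per SD). Active-arm use is then 2.3%, 3.9% and 7.9%.

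Sample size: 2 × 3.5² × (1.960 + 0.842)² / 1.0² ≈ 192.3, so 193 per arm.

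**Bias from keeping the scores.** Shortfall ≈ r × (placebo use − active use). For 10% use and r = 3: 3 × (0.100 − 0.079) = 0.063 points. Simulation (five visits, correlation 0.6, 4,000 runs per setting) agrees. In the table, W8 means use driven by Week 8 pain and W12 means use driven by Week 12 pain itself. Excluded scores are treated as missing in an MMRM-equivalent analysis.

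| Placebo / active use | Relief | Formula shortfall | Simulated, kept (W8 / W12) | Left after exclusion (W8 / W12) | Power kept → excluded, W8 | Power kept → excluded, W12 |
|---|---|---|---|---|---|---|
| 3% / 2.3% | 2 | 0.014 | 0.015 / 0.015 | 0.00 / 0.012 | 80.4 → 80.4 | 80.3 → 79.4 |
| 3% / 2.3% | 3 | 0.021 | 0.021 / 0.021 | 0.00 / 0.012 | 78.9 → 79.7 | 78.9 → 79.1 |
| 5% / 3.9% | 2 | 0.022 | 0.023 / 0.022 | 0.00 / 0.019 | 78.3 → 78.5 | 79.4 → 78.8 |
| 5% / 3.9% | 3 | 0.033 | 0.034 / 0.035 | 0.00 / 0.018 | 77.2 → 78.0 | 79.3 → 79.0 |
| 10% / 7.9% | 2 | 0.042 | 0.041 / 0.043 | 0.00 / 0.031 | 78.3 → 79.0 | 78.9 → 77.4 |
| 10% / 7.9% | 3 | 0.063 | 0.064 / 0.065 | 0.00 / 0.033 | 74.0 → 76.8 | 76.8 → 76.5 |

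The Monte Carlo standard error of each power figure is about 0.6 percentage points.

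**Steepness (10% use, 3 points relief).** At slope 0.5 the kept-score shortfall is 0.036; power goes 76.1 → 77.3 (W8) and 77.7 → 77.7 (W12). At slope 2 it is 0.098 (W8) and 0.095 (W12); power goes 74.1 → 78.7 and 78.3 → 77.1, and exclusion still leaves 0.074 in the W12 case.

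**Reading.** Exclusion removes the bias when use depends on pain already observed at Week 8, because missing at random then holds. It does not when use depends on the Week 12 pain that the excluded score would have measured. In those eight W12 settings power falls in six, is unchanged in one and rises by 0.2 points in one. Several of these changes are within simulation error, so the fair summary is no consistent gain.

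**Type I error.** With no true effect, 3 points of relief and 5% or 10% use, a false favourable result occurs in 2.3% to 2.5% of runs with scores kept and 2.4% to 2.5% with scores excluded, against a nominal 2.5%.

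**Scores affected.** 193 × (0.03 + 0.023) ≈ 10 to 193 × (0.10 + 0.079) ≈ 35, of 386.

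**The case for a change.** The strongest opposing argument is that the ITT rule cannot explain the asymmetry. Rescue near a visit is also a deviation, and the plan removes that score. Subjects enter on stable NSAID therapy that is then withdrawn, so relapse to an NSAID is plausible, and no planned analysis isolates the affected scores. Naming the strategy would cost one sentence.

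The asymmetry and the missing label stand. They do not make the primary analysis wrong. Rescue is a supplied, planned treatment with its own recording; prohibited drugs are controlled by prohibition, and different events may carry different strategies. The aim in 7.2 concerns rescue medication only.

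Extending the exclusion would not give consistency either. A rule for analgesics alone leaves corticosteroids and viscosupplementation, also in Table 2, untouched. A single 24-hour window for every drug sits awkwardly beside a washout defined in days or half-lives. The dropout-reason scenarios in SAP 16.1.5 are not written for one excluded score in a continuing subject.

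A related worry is that protocol 8.2.3 lists prohibited-medication use only under reasons not related to study treatment, so stopping the patch to take an analgesic for knee pain might miss the lack-of-efficacy handling. The text does not dictate this: the same section offers lack of efficacy and protocol deviation as treatment-related reasons.

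**Conclusion.** No change is called for. The observation is correct, but the rule for these scores can be read from the ITT definition, and what is missing is a label. Whether own-supply acetaminophen counts as rescue, and which record identifies it, are points analysts can settle sensibly at the blinded data review.

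Moving these scores to exclusion is a trade-off without a dependable benefit. Keeping them costs about 0.015 to 0.065 points of an assumed 1.0-point effect in the main settings, and up to 0.098 with very steep dependence on pain. Excluding them changes power by −1.5 to +2.8 percentage points in the main settings, and by up to +4.6 at the steepest slope. The sign depends on whether use follows earlier or current pain, and the excluded scores' missing-at-random assumption cannot be verified.

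This rests on assumed rates, relief and effect, and on use following pain in the same way in both arms. If HP-5000 subjects used more prohibited analgesics for some other reason, the bias would run in the drug's favour. The by-arm concomitant medication summary in SAP 13 would give a first indication of that, although it is not tied to the WOMAC window.
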